20.1. Premature Termination of the Study

Boston Scientific Corporation reserves the right to terminate the study at any stage but intends to exercise this right only for valid scientific or administrative reasons and reasons related to protection of subjects. Investigators, associated IRBs/ECs, and regulatory authorities, as applicable, will be notified in writing in the event of study termination.

20.1.1. Criteria for Premature Termination of the Study

Possible reasons for premature study termination include, but are not limited to, the following.

- The occurrence of unanticipated adverse device effects that present a significant or unreasonable risk to subjects enrolled in the study.
- An enrollment rate far below expectation that prejudices the conclusion of the study.
- A decision on the part of Boston Scientific to suspend or discontinue development of the device.

20.2. Termination of Study Participation by the Investigator or Withdrawal of IRB/ EC Approval

Any investigator or IRB in the iNod Feasibility Study may discontinue participation in the study or withdrawal approval of the study, respectively, with suitable written notice to Boston Scientific. Investigators, associated IRBs, and regulatory authorities, as applicable, will be notified in writing in the event of these occurrences.

20.3 Requirements for Documentation and Subject Follow-up

In the event of premature study termination a written statement as to why the premature termination has occurred will be provided to all participating centers by Boston Scientific. The IRB/EC and regulatory authorities, as applicable, will be notified. Detailed information on how enrolled subjects will be managed thereafter will be provided.

In the event an IRB terminates participation in the study, participating investigators, associated IRBs/ECs, and regulatory authorities, as applicable, will be notified in writing. Detailed information on how enrolled subjects will be managed thereafter will be provided by Boston Scientific.

In the event an investigator terminates participation in the study, study responsibility will be transferred to a co-investigator, if possible. In the event there are no opportunities to

transfer investigator responsibility; detailed information on how enrolled subjects will be managed thereafter will be provided by Boston Scientific.

The investigator must return all documents and investigational product to Boston Scientific, unless this action would jeopardize the rights, safety, or welfare of the subjects.

20.4 Criteria for Suspending/Terminating a Study Center

Boston Scientific Corporation reserves the right to stop the inclusion of subjects at a study center at any time after the study initiation visit if no subjects have been enrolled for a period beyond 3months after center initiation, or if the center has multiple or severe protocol violations/noncompliance without justification and/or fails to follow remedial actions.

In the event of termination of investigator participation, all study devices and testing equipment, as applicable, will be returned to BSC unless this action would jeopardize the rights, safety or well-being of the subjects. The IRB/EC and regulatory authorities, as applicable, will be notified. All subjects enrolled in the study at the center will continue to be followed through resolution of any procedure-related adverse events unless they are considered to endure in a chronic nature. The Principal Investigator at the center must make provision for these follow-up visits unless BSC notifies the investigational center otherwise.

21. Publication Policy

In accordance with the Corporate Policy on the Conduct of Human Subject Research, BSC requires disclosure of its involvement as a sponsor or financial supporter in any publication or presentation relating to a BSC study or its results. In accordance with the Corporate Policy for the Conduct of Human Subject Research, BSC will submit study results for publication (regardless of study outcome) following the conclusion or termination of the study. Boston Scientific Corporation adheres to the Contributorship Criteria set forth in the Uniform Requirements of the International Committee of Medical Journal Editors (ICMJE; <http://www.icmje.org>). In order to ensure the public disclosure of study results in a timely manner, while maintaining an unbiased presentation of study outcomes, BSC personnel may assist authors and investigators in publication preparation provided the following guidelines are followed.

1. All authorship and contributorship requirements as described above must be followed.
2. BSC involvement in the publication preparation and the BSC Publication Policy should be discussed with the Coordinating Principal Investigator(s) and/or Executive/Steering Committee at the onset of the project.

3. The First and Senior authors are the primary drivers of decisions regarding publication content, review, approval, and submission.

22. Bibliography

23.1 Abbreviations

Abbreviations are shown in table 23.1-1.

Table 23.1-1: Abbreviations

Acronym	Definition
ADE	Adverse Device Effect
AE	Adverse Event
CT	Computed Tomography
CXR	Chest X-Ray
DFU	Directions for Use
EBB	Endobronchial Biopsy
EBUS	Endobronchial Ultrasound
eCRF	Electronic Case Report Form
EC	Ethics Committee
EDC	Electronic Data Capture
FB	Flexible Bronchoscopy
FDA	Food and Drug Administration
GCP	Good Clinical Practices
IB	Investigator Brochure
ICF	Informed Consent Form
ICH	International Conference on Harmonization
IRB	Institutional Review Board
ISO	International Standards Organization
ITT	Intent-to-Treat
MDU	Motor Drive Unit
PP	Per-Protocol
PZT	Piezoelectric Transducer
R-EBUS	Radial Endobronchial Ultrasound
ROSE	Rapid On-Site Evaluation
SADE	Serious Adverse Device Effect
SAE	Serious Adverse Event
TBLB	Transbronchial Lung Biopsy
TBNA	Transbronchial Needle Aspiration
TTNA	Transthoracic Needle Aspiration
VATS	Video-Assisted Thorascopic Surgery
VB	Virtual Bronchoscopy

23.2. Definitions

Terms are defined in Table 23.2-1.

Table 23.2-1: Definitions

Term	Definition
SOURCE DATA	All information in original records and certified copies of original records of clinical finding, observations, or other activities in a clinical trial necessary for the reconstruction and evaluation of the trial. Source data are contained in the source documents (original records or certified copies).
SOURCE DOCUMENTS	Original documents, data, and records.

Abbreviations are defined in Table 23.1-1.

Revision History	11

PROTOCOL SUMMARY

Objective(s)	To demonstrate feasibility to access, visualize, and obtain specimens adequate for cytology of lung lesions in subjects with suspected lung cancer when using the iNod System.
Planned Indication(s) for Use	The iNod System is intended for use for diagnostic ultrasound imaging and ultrasound-guided fine needle aspiration (FNA) of extramural and submucosal lesions of the tracheobronchial tree.
Test Device	
The iNod System, is comprised of the following components:
 
 • iNod Ultrasound Imaging System • iNod Ultrasound Catheter • iNod Biopsy Needle • iNod Motor Drive Unit • iNod Sled 
The iNod Biopsy Needle and the iNod Ultrasound Catheter are intended to be used, in combination, in the Olympus BF-P190 or Olympus BF-MP160 Bronchoscopes.

Control Device	None
Study Design	Multi-center, Prospective, Single-arm Feasibility Study with Salvage.
Number of Subjects and Centers	
5 to 10 Subjects at 2-3 US study centers.
 
15 to 30 Subjects, across all study centers.

Primary Endpoint	
Clinical success is defined as the iNod System's ability to acquire adequate specimens of cellular matter suitable for the cytologic evaluation of targeted lung lesions, under real-time visualization.
 
Salvage Procedure: In case of primary endpoint failure with the iNod System, Radial EBUS-guided diagnostic sampling maneuvers (current standard-of-care) will be performed in an attempt to access, visualize, and sample targeted lung lesions.

Secondary Endpoints	
 1. Occurrence and severity of Adverse Events related to the iNod System biopsy procedures, as well as Adverse Events related to any subsequent Radial EBUS-guided salvage procedures. 2. Proportion of lesions visualized during iNod Maneuvers 3. Proportion of lesions accessed where iNod Biopsy Needles were deployed

Study Reference number E7113

	
in the target lesion during study maneuvers
 
4. Proportion of iNod maneuvers that acquire specimens of cellular matter for cytology

Follow-up Schedule	
Baseline Visit: Informed Consent, Medical History, including collection of a Chest CT image within 6 weeks of study procedure, which confirms the presence of peripheral pulmonary lesion(s).
 
Bronchoscopy Procedure: iNod sampling of lesion followed by additional standard of care (salvage) procedures, should collected specimens be determined as inadequate for cytologic evaluation. Intra-procedural specimens collected for cytology will be documented.
 
Completion / End of Study:
 
• Following the bronchoscopic procedure, and per standard clinical practice, the subject will have a post-procedure chest x-ray.• The subject will have a Day 7 Post-Procedure Safety Call to check for any delayed-onset Device/Procedure/Anesthesia-related safety events.
Study Duration	The study will close after enrollment is completed. The enrollment period is estimated to be open for approximately 1 year from First Patient In (FPI) through Last Patient Out (LPO). Follow-up of unforeseen procedure-related safety events could extend LPO beyond the date of the last study procedure.

1 INTRODUCTION

This statistical plan addresses the planned analyses for the iNod Feasibility Study based on protocol # 91122035. Specified analyses may be used for scientific presentations and/or manuscripts and may not all be provided to Regulatory Authorities.

2 ENDPOINT ANALYSIS

2.1 Primary Endpoint

The primary endpoint is clinical success defined as the iNod System's ability to acquire adequate specimens of cellular matter suitable for the cytologic evaluation of targeted lung lesions, under real-time visualization.

In case of primary endpoint failure with the iNod System, a salvage procedure will be performed using Radial EBUS-guided diagnostic sampling maneuvers (current standard-of-care) in an attempt to access, visualize, and sample targeted lung lesions.

2.1.1 Analysis

The primary analysis for clinical success will be descriptive for patients in the per-protocol (PP) analysis set.

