Imaging to be captured during the iNod System maneuvers, as identified with the serial number of the iNod Imaging System and iNod Biopsy Needle being utilized for each maneuver, will be collected as follows:

- Ultrasound image of the target lesion
- Ultrasound image of the deployed iNod Biopsy Needle at the target lesion
- Supplemental fluoroscopic images, if collected, should also be retained and similarly associated to the specific maneuver by documenting the serial number of the iNod Biopsy Needle being used for that specific procedure

Rapid on-site evaluation (ROSE) will be completed for all obtained specimens. Results will be associated with the serial number of the iNod Biopsy Needle being used for each unique specimen. ROSE interpretations, “adequate (for cytologic evaluation)” or “inadequate (for cytologic evaluation),” will be recorded. Collected specimens will undergo cytologic evaluation following the iNod procedure and final cytologic results will be reported in the study database.

The following situations would indicate the need to abandon the iNod System Procedure and proceed to salvage:

- If the iNod System is unable to physically reach the lesion, as evidenced by the absence of an ultrasound image of the lesion with the iNod System.
- If 3 separate aspirated specimens obtained from the target lesion with the iNod System result in “inadequate (for cytologic evaluation),” the investigator should stop iNod maneuvers and proceed to salvage.

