9.1. Endpoints

9.1.1. Primary Endpoint

Clinical success is defined as the iNod System's ability to acquire adequate specimens of cellular matter suitable for the cytologic evaluation of targeted lung lesions, under real-time visualization. The rate of Clinical Success will be calculated as the number of peripheral pulmonary lesions for which adequate cytologic specimens suitable for cytologic evaluation were obtained divided by the number of lesions the iNod System was attempted.

Hypotheses

There will be no formal statistical hypothesis tested since this is an observational study documenting the first human use of the iNod System

Sample Size

Enrollment is capped at 30 subjects with a maximum of 10 subjects per center. Since no formal hypothesis will be tested, there is no statistical justification of sample size.

Peripheral pulmonary lesions vary in their location in the tracheobronchial tree. Their size, characteristics (e.g., concentric vs. eccentric), and a sample size of 5-10 subjects per site allows greater potential to evaluate the usability and performance of the system for visualization and sampling this range of lesions.

Performance feedback for this traditional feasibility study is sought from more than 1 physician. While staying within the sample size confines of a traditional feasibility study, Boston Scientific has elected to seek the expertise of 2 to 3 interventional bronchoscopists.

Statistical Methods

Since no formal hypothesis is tested, only descriptive statistics will be used to summarize the primary endpoint.

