2.1.3 Statistical Methods

For the primary endpoint of clinical success, the analysis will be performed as described below.

For all PP patients, the primary endpoint of clinical success occurs when there is at least one adequate specimen of cellular matter suitable for the cytologic evaluation of targeted lung lesions is acquired under real-time visualization by the iNod System. If there is no adequate specimen of cellular matter suitable for the cytologic evaluation of targeted lung lesions, under real-time visualization by the iNod System, then the patient will be considered a clinical failure. The primary endpoint will be evaluated as the number of clinical successes out of all PP patients; a 95% exact confidence interval will also be calculated for the primary endpoint.

For patients who do not have clinical success and a salvage procedure is done, the proportion of patients with a salvage procedure for which at least one adequate specimen of cellular matter suitable for the cytologic evaluation of targeted lung lesions will be calculated; a 95% exact

Boston Scientific
iNod Feasibility SAP
91154618 Rev/Ver AA
Page 5 of 11

confidence interval will also be calculated for the proportion of patients with a successful salvage procedure.

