3.2.2 Per Protocol Cohort

The per-protocol (PP) cohort is a subset of the ITT subjects for whom a specimen was obtained using the iNod System.

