6.3.2 Per-protocol patients

A subject is in the PP cohort if the subject is in the ITT cohort and at least one specimen was obtained using the iNod System.

Valid Data Sources

- ITT cohort subjects
- iNod Diagnostic Procedure Form

Valid Data Points:

- ITT cohort subjects
- iNod Diagnostic Procedure Form:

- “Was a sample obtained?”

Analysis approach:

- **Include** a subject in the PP cohort if **all the following conditions are met:**
 - Subject is in the ITT cohort
 - “Was a sample obtained?” is “Yes”
- **Exclude** a subject from the PP cohort if **one of the following conditions are met:**
 - Subject is not in the ITT cohort
 - “Was a sample obtained?” is “No” or missing

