6.3.4 Primary endpoint

The primary endpoint is clinical success defined as the iNod System’s ability to acquire adequate specimens of cellular matter suitable for the cytologic evaluation of targeted lung lesions, under real-time visualization.

Valid Data Sources

- PP cohort subjects
- iNod Diagnostic Procedure Form

Valid Data Points

- PP cohort subjects
- iNod Diagnostic Procedure Resection form: “If yes, was it adequate for Rapid On-Site Evaluation (ROSE) Diagnosis/Cytology?” following the question “Was a sample obtained?” on the same form

Analysis approach:

- Include subject in the **denominator** if **both of the following conditions are met**:
 - Subject is in the PP cohort
 - “If yes, was it adequate for Rapid On-Site Evaluation (ROSE) Diagnosis/Cytology?” is answered “Yes” or “No”
- Include subject in the **numerator** if **both of the following conditions are met**:
 - Subject is in the PP cohort
 - “If yes, was it adequate for Rapid On-Site Evaluation (ROSE) Diagnosis/Cytology?” is answered “Yes”

REVISION HISTORY

Document Revision Number	Template Number and Version	Section	Change	Reason for Change
AA	90702621, AC	All	Original version of the SAP	

Boston Scientific
iNod Feasibility SAP
91154618 Rev/Ver AA
Page 11 of 11

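### The SAP computes the primary success rate only among subjects who yielded an iNod specimen, whereas the protocol divides by all lesions attempted, so attempts that yield nothing are dropped instead of counted as failures.

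*SAP*

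**What the plan says.** Protocol 9.1.1 gives the denominator of the clinical success rate directly: lesions with adequate specimens are "divided by the number of lesions the iNod System was attempted".

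The SAP uses a different one. Section 2.1.1 states: "The primary analysis for clinical success will be descriptive for patients in the per-protocol (PP) analysis set". Section 2.1.3 repeats it: "The primary endpoint will be evaluated as the number of clinical successes out of all PP patients", with an exact 95% confidence interval. SAP 3.2.2 defines the per-protocol (PP) cohort as "a subset of the ITT subjects for whom a specimen was obtained using the iNod System", and Protocol 9.2.1 defines it the same way. The programming rule in SAP 6.3.2 requires that "at least one specimen was obtained using the iNod System" and excludes a subject whose sample-obtained field is No or missing. SAP 6.3.4 then builds both numerator and denominator from PP subjects, using the form question on whether the sample "was it adequate for Rapid On-Site Evaluation (ROSE) Diagnosis/Cytology".

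Two other passages bear on how an attempt without a specimen should be treated. Protocol 8.5 lists reasons to abandon iNod and go to salvage, the first being "If the iNod System is unable to physically reach the lesion". SAP 2.1 says what salvage follows: "In case of primary endpoint failure with the iNod System, a salvage procedure will be performed".

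**The concern.** The objective in both documents is to show that lesions can be accessed, visualized and sampled. A rate computed only among subjects who gave a specimen conditions on part of what the study sets out to show. An attempted subject with no specimen goes to salvage, which the documents describe as the consequence of primary endpoint failure, yet never enters the primary rate. A subject whose specimens are all inadequate stays in and counts as a failure. The less complete failure is counted and the more complete one is not.

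The same data can therefore give two different primary results depending on which document is followed, and under the conditions set out below the SAP version is never the less favourable to the device. SAP section 1 foresees use of the analyses in presentations and manuscripts, so the figure may be quoted outside the study.

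**Working it through.** **Which set matches the protocol denominator?**

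| Set | Membership | Matches attempted? |
|---|---|---|
| ITT (SAP 3.2.1, 6.3.1) | Signed and dated consent | No. It includes subjects withdrawn before the iNod procedure, a case Protocol 7.2 provides for |
| PP (SAP 3.2.2, 6.3.2) | ITT with at least one iNod specimen | No. It omits attempts with no specimen |
| Restricted PP (SAP 3.2.3, 6.3.3) | PP with proper consent and all eligibility criteria met | No, for the same reason |

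No defined set is the attempted set. SAP 3.1 promises descriptive statistics for ITT and PP in general, but no ITT success rate is specified and 6.3.4 programs PP only.

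**Size of the difference.** The plan states no expected success rate or expected number of attempts without a specimen, so there is no figure to reproduce. Let N be the subjects attempted, k those with no iNod specimen, b those with only inadequate specimens, and s = N - k - b the successes. Assume one lesion per subject and no missing adequacy answers.

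- Protocol rate = s/N
- SAP rate = s/(N - k)
- Ratio of SAP to protocol = N/(N - k), which is at least 1, and above 1 when k > 0

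N = 15 and N = 30 are the planned limits. The values of k and b are assumed. Intervals are exact (Clopper-Pearson) 95%.

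| N | b | k | SAP rate | Protocol rate | Gap (points) |
|---|---|---|---|---|---|
| 30 | 3 | 0 | 27/30 = 90.0% (73.5-97.9) | 27/30 = 90.0% (73.5-97.9) | 0 |
| 30 | 3 | 1 | 26/29 = 89.7% (72.6-97.8) | 26/30 = 86.7% (69.3-96.2) | 3.0 |
| 30 | 3 | 3 | 24/27 = 88.9% (70.8-97.6) | 24/30 = 80.0% (61.4-92.3) | 8.9 |
| 30 | 3 | 6 | 21/24 = 87.5% (67.6-97.3) | 21/30 = 70.0% (50.6-85.3) | 17.5 |
| 15 | 1 | 0 | 14/15 = 93.3% (68.1-99.8) | 14/15 = 93.3% (68.1-99.8) | 0 |
| 15 | 1 | 1 | 13/14 = 92.9% (66.1-99.8) | 13/15 = 86.7% (59.5-98.3) | 6.2 |
| 15 | 1 | 3 | 11/12 = 91.7% (61.5-99.8) | 11/15 = 73.3% (44.9-92.2) | 18.3 |

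In the N = 30 rows, as k goes from 0 to 6 the protocol rate falls 90.0 - 70.0 = 20.0 points while the SAP rate falls 90.0 - 87.5 = 2.5 points. The SAP rate is nearly insensitive to attempts that yield nothing.

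The limiting case is b = 0, where every specimen obtained is adequate. The SAP then reports 100% however many attempts yield none: with N = 30 and k = 6, 24/24 = 100% (85.8-100) against 24/30 = 80.0% (61.4-92.3).

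**Two smaller mismatches.** The protocol counts lesions and the SAP counts patients. SAP 6.3.4 keeps in the denominator only PP subjects whose adequacy question is answered Yes or No, whereas 2.1.3 speaks of all PP patients.

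**The case against.** The strongest argument is about importance. There is no hypothesis, success threshold or formal interim decision, so the consequence is which descriptive percentage is called primary in a study of 15 to 30 subjects. Access failures would not be wholly hidden: secondary endpoints 2 and 3 report lesions visualized and lesions accessed with the needle deployed, and Protocol 8.5 identifies an unreachable lesion by the absence of an ultrasound image. This stands as a limit on the consequences. It does not repair the primary rate or its interval, and the SAP gives no denominators for those secondary proportions.

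A second argument is that the protocol does not define an attempt. If it meant attempted sampling, lesions never reached would fall outside the protocol denominator too, and the gap would shrink to cases where the needle was deployed and nothing obtained. The salvage wording favours the broader reading, but the definition is missing and should be supplied. Relatedly, the dropped subjects include access failures but need not all be such: a lesion may be reached and yield nothing. How sites would code an empty aspirate is not visible in the documents; if coded as a sample that was inadequate, fewer subjects drop out.

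Third, the large gaps need 20% of attempts to yield no specimen (6 of 30, or 3 of 15). At 1 of 30 the gap is 3.0 points, and the paired intervals overlap widely. This is fair, and the counts are scenarios only.

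Finally, eligibility and the stopping rules refer to a single target lesion, so lesion and patient counts will usually coincide. The unit point is a matter of aligning wording.

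**Conclusion.** The concern holds. The SAP's primary denominator contradicts Protocol 9.1.1, and nothing elsewhere in either document reconciles them. With one lesion per subject and no missing adequacy answers, the SAP rate exceeds the protocol rate by the factor N/(N-k) whenever there is at least one success and one attempted subject without a specimen: 1.11 for 3 of 30, and 1.25 for 6 of 30 or 3 of 15. The rates agree if every attempt yields a specimen, or if there are no successes. The actual size cannot be known from the documents. No formal decision depends on it, but it should be corrected before analysis because it changes the study's primary result and, under those assumptions, can only favour the device.

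**What to change.** Amend SAP 2.1.1, 2.1.3 and 6.3.4 so that the primary analysis set is all subjects (target lesions) in whom iNod was attempted, and add that set to SAP 3.2.

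- Define an attempt. One option already recorded is the start of the first iNod maneuver, which Protocol 8.5 times from introduction of the biopsy needle catheter pre-loaded with the ultrasound catheter.
- Count a lesion not reached, no specimen, or no documented adequate specimen as failure. The last extends to missing adequacy answers the SAP 2.1.3 rule that a patient without an adequate specimen is a failure, and removes the conflict between 2.1.3 and 6.3.4.
- Keep the exact 95% interval, and show the PP result as supportive.
- Use one unit, lesion or patient, in both documents.
- As a clarification, state that the salvage proportion covers all attempted non-successes who had salvage.

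The cost is SAP wording and a small programming change. The maneuver, sample-obtained and adequacy fields are already collected, and no patients are added. The only downside is that the reported rate may be less favourable.
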